12.2. Subgroup analyses

Not Applicable.

12.3. Pharmacokinetic analysis

The PK analysis will be performed on the PK population.

MEN1611 plasma concentrations will be summarized by cohort, cycle, visit, day, nominal time point using the following descriptive statistics:

- Number of non-missing observations (n)

- Arithmetic mean, standard deviation (SD), coefficient of variation (CV%)
- Geometric mean (GM), Geometric SD and Geometric CV%
- Minimum, median and maximum

For the descriptive statistics, concentration values which are BLOQ will be set to 0.

MEN1611 concentration values below the lower limit of quantification (BLOQ) will be reported as "BLOQ" in the listing of PK concentrations.

13. Tables, listings and figures

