3.1. Changes from study protocol

All analyses detailed in this document are as specified in the protocol and subsequent amendments, no major changes from the protocol-planned primary analysis have been performed. The only exception is the PK data analysis, for which no estimation of individual PK parameters will be conducted by using a population PK approach. Plasma concentrations of MEN1611 by time-point will be summarised by descriptive statistics only.

4. Study overview

MEN1611 is a potent and selective Class I PI3K inhibitor with a novel structure. In particular, it has potent inhibitory activities against Class I PI3K α . MEN1611 is yellow to greenish yellow powder or powder with lumps, stable in the solid state. The MEN1611 drug product is a hard capsule for oral administration.

This study is designed as an Open-label, Multicenter, Phase Ib/II Study of MEN1611 and Cetuximab, to be conducted in approximately 29 sites in Europe and US.

Phosphatidylinositol 3-kinase, catalytic, alpha polypeptide gene (PIK3CA) mutated, N-K-RAS and BRAF wild type, metastatic colorectal cancer, in patients failing irinotecan, oxaliplatin, 5-FU and anti- epidermal growth factor receptor (EGFR) containing regimens will be enrolled.

The study is aimed to determine the RP2D of MEN1611 when administered orally in combination with cetuximab during the first step of the study, and to assess the anti-tumor activity of MEN1611 in combination with cetuximab during the second step.

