5.4.2. Secondary endpoints

- *Safety and tolerability:*
 - Incidence, severity as per CTCAE v. 5.0 grading, seriousness and treatment-causality of TEAEs.
 - Frequency of clinically significant abnormalities in physical examination, safety laboratory tests, urinalysis, vital signs and 12-lead ECG.
- *PK profile:* MEN1611 plasma concentration-time data will be summarised descriptively.
- *Disease Control Rate (DCR)* defined as percentage of patients whose disease shrinks or remains stable over a certain time period. DCR is the sum of the BOR of complete, partial and stable disease rates according to local assessment.
- *Objective Response Rate (ORR)* defined as percentage of patients who had a BOR of complete response (CR), or (PR) partial response to therapy.
- *Duration of response* defined as time from first occurrence of a BOR of PR, CR or SD as locally assessed, until the disease has been shown to progress following treatment. Subjects, with a previous response, who do not show a relapse or die without recording a relapse are censored at their last available relapse-free tumor assessment date. Subjects with only one tumor assessment after baseline showing a PD, are not included in the calculation. Please refer to Attachment A for the complete Censoring Rules list.
- *Progression Free Survival:* Defined as the number of days between the first study treatment

administration to the date of first documented disease progression as per local assessment, relapse or death from any cause. Responding patients and patients who are lost to follow-up are censored at their last tumour assessment date. Please refer to Attachment A for the complete Censoring Rules list.

- *Overall Survival:* Defined as the number of days between the first study treatment administration and death from any cause. Patients still alive, that have withdrawn the study, are censored using the latest among end of study and follow-up dates. Drop-out patients are considered censored and the last available date in which the subject is known to be alive will be considered.

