Table 2.10: Overall summary of Coagulation Laboratory Parameters by Visit and Cohort

Table 2.11: Overall summary of Urinalysis Laboratory Parameters by Visit and Cohort

Table 2.12: Overall summary of 12-lead ECG Parameters by Visit and Cohort

Table 2.13: Overall summary of ECOG Performance Status by Visit and Cohort

Table 2.14: Overall summary of Physical Examination Parameters by Visit and Cohort

Table 2.15: Overall summary of Vital Signs by Visit and Cohort

EFFICACY ANALYSIS

Table 3.1.1: Summary of Tumor Response Endpoints – Local radiology assessment according to RECIST by Cohort

Table 3.1.2: Summary of Tumor Response Endpoints – Central radiology assessment according to RECIST by Cohort

Table 3.2.1: Overall Response Rate by Timepoint – Local radiology assessment according to RECIST 1.1 by Cohort

Table 3.2.2: Overall Response Rate by Timepoint – Central radiology assessment according to RECIST 1.1 by Cohort

Table 3.3: Summary of Time to Event Endpoints by Cohort

PHARMACOKINETIC ANALYSIS

Table 4.1: Summary statistics of MEN1611 PK concentrations by cohort, cycle, visit, nominal time point

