13.2.2. Listings

Listing 5.1: Demographic Characteristics

Listing 5.2: Reason of treatment withdrawal

Listing 5.3: Reason of study withdrawal

Listing 5.4: Tumor History Characteristics

Listing 5.5: Tumor History Previous Treatment

Listing 5.6: Medical History

Listing 5.7: Prior and Concomitant Medications

Listing 5.8: Procedures

Listing 5.9: Dose-Limiting Toxicities

Listing 5.10: Adverse Events

Listing 5.11: Treatment Emergent Adverse Events

Listing 5.12: Related Treatment Emergent Adverse Events

Listing 5.13: Serious Treatment Emergent Adverse Events

Listing 5.14: Serious and Related Treatment Emergent Adverse Events
Listing 5.15: Haematology
Listing 5.16: Biochemistry
Listing 5.17: Coagulation
Listing 5.18: Urinalysis
Listing 5.19: Virology
Listing 5.20: 12-lead ECG
Listing 5.21: ECOG Performance Status
Listing 5.22: Physical Examination
Listing 5.23: Vital Signs
Listing 5.24: Pregnancy test
Listing 5.25: Treatment Intake – MEN1611
Listing 5.26: Treatment Intake – Cetuximab
Listing 5.27: Tumor Lesion – Local assessment
Listing 5.28: Tumor Lesion – Central assessment
Listing 5.29: Tumor Response by Timepoint – Local assessment according to RECIST
Listing 5.30: Tumor Response by Timepoint – Central assessment according to RECIST
Listing 5.31: PK concentrations

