13.2.1. Figures

Figure 6.1: Kaplan-Meier Curve of Duration of Response – Local Assessment
Figure 6.2: Kaplan-Meier Curve of Duration of Response – Central Assessment
Figure 6.3: Kaplan-Meier Curve of Progression-Free Survival – Local Assessment
Figure 6.4: Kaplan-Meier Curve of Progression-Free Survival – Central Assessment
Figure 6.5: Kaplan-Meier Curve of Overall Survival
Figure 6.6: Individual Concentration-time curves (linear scale)

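### SAP 12.3 sets concentrations below the quantification limit to 0 for the geometric statistics too, which makes the geometric mean 0 and leaves the geometric SD and CV% undefined in any affected cell

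*SAP*

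**What the plan says.** SAP section 12.3 summarises MEN1611 plasma concentrations by cohort, cycle, visit, day and nominal time point. Its list of statistics starts with "Number of non-missing observations (n"), continues with the arithmetic mean, SD and CV%, then "Geometric mean (GM), Geometric SD and Geometric CV"%, and ends with the minimum, median and maximum. The rule for low values follows: "For the descriptive statistics, concentration values which are BLOQ will be set to 0". The only other BLOQ sentence in that section concerns how such values appear in the listing.

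Neither SAP section 11.3 (data imputation) nor Protocol section 9.3.2 (pharmacokinetic analysis) gives a different BLOQ rule.

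The PK profile is a secondary endpoint, and SAP section 5.4.2 describes its analysis as follows: "MEN1611 plasma concentration-time data will be summarised descriptively". SAP section 3.1 drops the population PK approach planned in the protocol and states: "Plasma concentrations of MEN1611 by time-point will be summarised by descriptive statistics only". The planned PK outputs are "Table 4.1: Summary statistics of MEN1611 PK concentrations by cohort, cycle, visit, nominal time point", "Listing 5.31: PK concentrations" and "Figure 6.6: Individual Concentration-time curves (linear scale").

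**The concern.** The geometric mean, SD and CV% are functions of the logarithm of the concentration, and the logarithm of 0 does not exist. The section lists these statistics and then applies a substitution under which they cannot be computed. A programmer who meets a BLOQ value must therefore either print a geometric mean of 0 with two blanks, or depart from the written rule in a way the SAP does not specify.

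What is at stake is how Table 4.1 reads. It is the only PK summary table in the SAP, now that the population model has been dropped. The outcome that could mislead is the quiet one: log(0) becomes missing, and the geometric statistics come from fewer samples than the n printed beside them.

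**Working it through.** The documents give no figure on this point, so there is nothing to reproduce. The check is algebraic, with an illustration.

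**Definitions**, for n concentrations x:
- geometric mean (GM) = (product of x)^(1/n) = exp(mean of ln x)
- geometric SD = exp(SD of ln x)
- geometric CV% = 100 × sqrt(exp((SD of ln x)²) − 1)

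**One value set to 0.** The product is 0, so GM = 0. Since ln 0 has no finite value, the SD of ln x does not exist, and the geometric SD and geometric CV% are undefined. This holds whatever the other values are.

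**Illustration.** The values are invented, for a small cell of six patients: BLOQ, 10, 20, 30, 40, 60.

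| Statistic | Rule as written | If log(0) becomes missing |
|---|---|---|
| n printed | 6 | 6 |
| Minimum | 0 | 0 |
| Median | 25 | 25 |
| Arithmetic mean | 160/6 = 26.7 | 26.7 |
| GM | 0 | 14,400,000^(1/5) = 27.0 (5 samples) |
| Geometric SD | undefined | 1.98 (5 samples) |
| Geometric CV% | undefined | 77.5 (5 samples) |

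The same data give two different rows, and the SAP does not say which one to print. In the right-hand column the geometric statistics rest on 5 samples beside n = 6. The minimum of 0 tells the reader that at least one value was BLOQ. The number of BLOQ values does not appear among the listed statistics.

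**How often a cell is affected.** One BLOQ value is enough. With assumed BLOQ rate r, independent values and cell size n, the chance of at least one is 1 − (1 − r)^n:
- n = 6, r = 1%: 5.9%
- n = 20, r = 5%: 64.2%
- n = 40, r = 10%: 98.5%

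These rates and cell sizes show a range only. The readable text does not give the quantification limit, the BLOQ rate or the PK sampling times.

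**Bias of the quantifiable-only GM.** Assume lognormal concentrations with BLOQ share p in the lower tail. With s = sqrt(ln(1 + CV²)) and z = Φ⁻¹(p), the ratio to the true GM is exp(s × φ(z)/(1 − p)). For CV 60%, s = 0.555; for CV 100%, s = 0.833.

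| BLOQ share | CV 60% | CV 100% |
|---|---|---|
| 5% | 1.06 | 1.09 |
| 40% | 1.43 | 1.71 |

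**The case against.** The strongest reply is that little depends on this. PK is descriptive here, and no hypothesis or primary endpoint uses Table 4.1. A geometric mean of 0 beside a positive median would be noticed. Even if values were dropped quietly, the minimum of 0 flags the cell, and the listing shows each BLOQ value as such. The protocol also refers to a PK Data Analysis Plan, which is not available and may deal with BLOQ values. The table shells are not shown either, so a BLOQ count could still be added. There may be few affected cells, or none.

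All of that stands as a limit on size. It does not remove the defect: the SAP contains an explicit rule for its own table, and that rule fails for three of the statistics it covers. A different rule in the PK Data Analysis Plan would conflict with SAP 12.3 and would need reconciling.

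Three stronger readings are tempting but not supported:

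- *A reader might infer that the zero rule also invalidates the arithmetic statistics.* It does not. They remain defined and computable, and the fix below keeps the rule for them.
- *A reader might infer from the illustration that the table would typically show a GM above the arithmetic mean (27.0 against 26.7).* That is a small-cell effect. In simulated lognormal cells where the single lowest value is set to 0 in the mean and left out of the GM, it occurs in about 91% (CV 60%) and 58% (CV 100%) of cells at n = 6. At n = 20 it occurs in about 2% and under 0.1%, and at n = 40 in essentially none.
- *A reader might infer that dose confirmation rests on the faulty summary, because the Data Safety Committee reviews Step 1 PK data.* SAP 7.4.1 says the committee receives its data under a separate Data Review Plan. Nothing shows that it uses Table 4.1.

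**Conclusion.** The point holds as a minor defect in the wording of SAP 12.3. In any Table 4.1 cell with at least one BLOQ value, the stated rule gives a geometric mean of 0 and no geometric SD or CV%. This conclusion is algebraic and needs no assumption about the data. Under the alternative in which log(0) becomes missing, the geometric statistics would rest on fewer samples than the printed n. The minimum of 0 would disclose that a BLOQ value is present, but not the count.

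The practical size is unknown, because the frequency of BLOQ values cannot be derived from the readable text. It is bounded by the table's role as a descriptive secondary output, with individual values still available in Listing 5.31 and Figure 6.6.

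**What to change.** Amend SAP 12.3 before database lock:

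1. Limit the substitution of 0 to the arithmetic and order statistics.
2. Compute the geometric mean, SD and CV% on quantifiable samples only, print the n they rest on, and show them as not calculable where too few samples are quantifiable.
3. Print the number of BLOQ samples per time point in Table 4.1.

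The cost is a few sentences and a change to one table program. The drawback is that a geometric mean from quantifiable samples only is too high, by the factors in the last table of the working (about 1.06 to 1.09 at 5% BLOQ and 1.43 to 1.71 at 40%, under the assumed lognormal). The printed BLOQ count lets readers judge this.

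Substituting half the quantification limit for BLOQ values, or a fixed BLOQ share above which nothing is shown, are competing conventions rather than required corrections. The first is sensitive to the limit itself: in the six-patient illustration the geometric CV is 116% if the limit is 10 and 444% if it is 1. Whichever rule is chosen should be written down in advance.

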13.1. Statistical Analysis Report

The TLF (Tables, Listings and Figures) will follow the list of tables, plots, and listings agreed with the Study Physician. The SAR will follow the list of tables, plots, and listings listed in the following section. The index is intended to provide the overall idea of the general output and ordering of the SAR, it will not necessarily be reproduced in the SAR.

13.2. Index of TLFs

13.2.1. Tables

PATIENT DISPOSITION AND BASELINE TABLES

Table 1.1: Enrolment Status

Table 1.2: Overall Patients Disposition by Cohort

Table 1.3: Reasons of treatment withdrawal by Cohort

Table 1.4: Reasons of study withdrawal by Cohort

Table 1.5: Demographic Characteristics by Cohort

Table 1.6: Disease and Baseline Characteristics by Cohort

Table 1.7: Medical History by System Organ Class and Preferred Term by Cohort

Table 1.8: Current Medical Conditions by System Organ Class and Preferred Term by Cohort

Table 1.9: Anti-Cancer Medication by ATC Code by Cohort

Table 1.10: Prior Medication by ATC Code by Cohort

Table 1.11: Concomitant Medication by ATC Code by Cohort

Table 1.12: Prior and Concomitant Medication by ATC Code by Cohort

Table 1.13: Procedures History by System Organ Class and Preferred Term by Cohort

Table 1.14: Concomitant Procedures by System Organ Class, Preferred Term and Cohort

Table 1.15: Prior Radiotherapy by Cohort

Table 1.16: Substance Use by Cohort

Table 1.17: Overall summary of Virology by Cohort

SAFETY ANALYSIS

Table 2.1: Treatment Exposure and Compliance by Cohort

Table 2.2: Adverse Events Summary by Cohort

Table 2.2.1: Adverse Events by System Organ Class, Preferred Term and Cohort

Table 2.2.2: Serious Adverse Events by System Organ Class, Preferred Term and Cohort
Table 2.2.2: Related Adverse Events by System Organ Class, Preferred Term and Cohort
Table 2.2.2: Serious and Related Adverse Events by System Organ Class, Preferred Term and Cohort
Table 2.3: Treatment Emergent Adverse Events Summary by Cohort
Table 2.3.1: Treatment Emergent Adverse Events by System Organ Class, Preferred Term and Cohort
Table 2.3.2: Treatment Emergent Adverse Events by Grade, System Organ Class, Preferred Term and Cohort
Table 2.3.3.1: Treatment Emergent Adverse Events leading to Drug Interruption by System Organ Class, Preferred Term and Cohort
Table 2.3.3.2: Treatment Emergent Adverse Events leading to Drug Withdrawal by System Organ Class, Preferred Term and Cohort
Table 2.3.3.3: Treatment Emergent Adverse Events leading to Dose Modification by System Organ Class, Preferred Term and Cohort
Table 2.3.3.4: Treatment Emergent Adverse Events leading to Death by System Organ Class, Preferred Term and Cohort
Table 2.4.1: Related Treatment Emergent Adverse Events by System Organ Class, Preferred Term and Cohort
Table 2.4.2: Related Treatment Emergent Adverse Events by Grade, System Organ Class, Preferred Term and Cohort
Table 2.4.3.1: Related Treatment Emergent Adverse Events leading to Drug Interruption by System Organ Class, Preferred Term and Cohort
Table 2.4.3.2: Related Treatment Emergent Adverse Events leading to Drug Withdrawal by System Organ Class, Preferred Term and Cohort
Table 2.4.4.3: Related Treatment Emergent Adverse Events leading to Dose Modification by System Organ Class, Preferred Term and Cohort
Table 2.4.4.4: Related Treatment Emergent Adverse Events leading to Death by System Organ Class, Preferred Term and Cohort
Table 2.5.1: Serious Treatment Emergent Adverse Events by System Organ Class, Preferred Term and Cohort
Table 2.5.2: Serious Treatment Emergent Adverse Events by Grade, System Organ Class, Preferred Term and Cohort
Table 2.5.3.1: Serious Treatment Emergent Adverse Events leading to Drug Interruption by System Organ Class, Preferred Term and Cohort
Table 2.5.3.2: Serious Treatment Emergent Adverse Events leading to Drug Withdrawal by System Organ Class, Preferred Term and Cohort
Table 2.5.3.3: Serious Treatment Emergent Adverse Events leading to Dose Modification by System Organ Class, Preferred Term and Cohort
Table 2.5.3.4: Serious Treatment Emergent Adverse Events leading to Death by System Organ Class, Preferred Term and Cohort
Table 2.6.1: Serious and Related Treatment Emergent Adverse Events by System Organ Class, Preferred Term and Cohort
Table 2.6.2: Serious and Related Treatment Emergent Adverse Events by Grade, System Organ Class, Preferred Term and Cohort
Table 2.6.3.1: Serious and Related Treatment Emergent Adverse Events leading to Drug Interruption by System Organ Class, Preferred Term and Cohort

Table 2.6.3.2: Serious and Related Treatment Emergent Adverse Events leading to Drug Withdrawal by System Organ Class, Preferred Term and Cohort

Table 2.6.3.3: Serious and Related Treatment Emergent Adverse Events leading to Dose Modification by System Organ Class, Preferred Term and Cohort

Table 2.6.3.4: Serious and Related Treatment Emergent Adverse Events leading to Death by System Organ Class, Preferred Term and Cohort

Table 2.7: Dose Limiting Toxicities by System Organ Class, Preferred Term and Cohort

Table 2.8: Overall summary of Haematology Laboratory Parameters by Visit and Cohort

Table 2.9: Overall summary of Biochemistry Laboratory Parameters by Visit and Cohort

Table 2.10: Overall summary of Coagulation Laboratory Parameters by Visit and Cohort

Table 2.11: Overall summary of Urinalysis Laboratory Parameters by Visit and Cohort

Table 2.12: Overall summary of 12-lead ECG Parameters by Visit and Cohort

Table 2.13: Overall summary of ECOG Performance Status by Visit and Cohort

Table 2.14: Overall summary of Physical Examination Parameters by Visit and Cohort

Table 2.15: Overall summary of Vital Signs by Visit and Cohort

EFFICACY ANALYSIS

Table 3.1.1: Summary of Tumor Response Endpoints – Local radiology assessment according to RECIST by Cohort

Table 3.1.2: Summary of Tumor Response Endpoints – Central radiology assessment according to RECIST by Cohort

Table 3.2.1: Overall Response Rate by Timepoint – Local radiology assessment according to RECIST 1.1 by Cohort

Table 3.2.2: Overall Response Rate by Timepoint – Central radiology assessment according to RECIST 1.1 by Cohort

Table 3.3: Summary of Time to Event Endpoints by Cohort

PHARMACOKINETIC ANALYSIS

Table 4.1: Summary statistics of MEN1611 PK concentrations by cohort, cycle, visit, nominal time point

13.2.2. Listings

Listing 5.1: Demographic Characteristics

Listing 5.2: Reason of treatment withdrawal

Listing 5.3: Reason of study withdrawal

Listing 5.4: Tumor History Characteristics

Listing 5.5: Tumor History Previous Treatment

Listing 5.6: Medical History

Listing 5.7: Prior and Concomitant Medications

Listing 5.8: Procedures

Listing 5.9: Dose-Limiting Toxicities

Listing 5.10: Adverse Events

Listing 5.11: Treatment Emergent Adverse Events

Listing 5.12: Related Treatment Emergent Adverse Events

Listing 5.13: Serious Treatment Emergent Adverse Events

Listing 5.14: Serious and Related Treatment Emergent Adverse Events
Listing 5.15: Haematology
Listing 5.16: Biochemistry
Listing 5.17: Coagulation
Listing 5.18: Urinalysis
Listing 5.19: Virology
Listing 5.20: 12-lead ECG
Listing 5.21: ECOG Performance Status
Listing 5.22: Physical Examination
Listing 5.23: Vital Signs
Listing 5.24: Pregnancy test
Listing 5.25: Treatment Intake – MEN1611
Listing 5.26: Treatment Intake – Cetuximab
Listing 5.27: Tumor Lesion – Local assessment
Listing 5.28: Tumor Lesion – Central assessment
Listing 5.29: Tumor Response by Timepoint – Local assessment according to RECIST
Listing 5.30: Tumor Response by Timepoint – Central assessment according to RECIST
Listing 5.31: PK concentrations

13.2.1. Figures

Figure 6.1: Kaplan-Meier Curve of Duration of Response – Local Assessment
Figure 6.2: Kaplan-Meier Curve of Duration of Response – Central Assessment
Figure 6.3: Kaplan-Meier Curve of Progression-Free Survival – Local Assessment
Figure 6.4: Kaplan-Meier Curve of Progression-Free Survival – Central Assessment
Figure 6.5: Kaplan-Meier Curve of Overall Survival
Figure 6.6: Individual Concentration-time curves (linear scale)
